### RESEARCH OBJECTIVES:

Exposure-based cognitive-behavioral therapy (CBT) is highly efficacious and a front-line treatment for anxiety disorders and obsessive-compulsive disorder. Despite clear efficacy, exposure therapy remains one of the least utilized EBPs to treat anxiety. Even among providers with specialized training in exposure, less than half report use with anxious patients. This suggests our current training paradigms for exposure therapy require a shift, incorporating innovative theory-driven approaches capable of addressing barriers to dissemination.

Effective therapist training capable of changing therapist behavior is a core component in the dissemination of EBPs. Experiential activities (e.g., role-play) are more likely to produce a change in therapist practice as compared to passively delivered didactic instruction. Virtual training environments are well-equipped to overcome issues related to representativeness, replicability, individualization, standardization and economic scalability, all of which limit the efficacy and reach of role playing and other (non-technological) experiential training tasks. To our knowledge, virtual reality (VR) has yet to be leveraged as an experiential training strategy for promoting the delivery of psychotherapeutic strategies. VR platforms have strong support for their efficacy in treating patient anxiety. Accordingly, VEs may be especially successful in promoting “exposure to exposure” during the training of exposure therapists.

This study will develop **SET™** utilizing simulated interactions with an anxious VP to target and reduce therapist negative beliefs about exposure. **SET™** will be developed to be delivered via two media methods: Head Mounted Display (HMD; hypothesized as high-immersion) and a web-based (WB; via laptop or mobile device; hypothesized as low-immersion). The goal is to test which platform provides an ideal balance of usability, target engagement (i.e., negative belief change), and scalability.

### SUBJECT RECRUITMENT:

**Study setting.** Study procedures will take place at Bradley Hospital.

**Participants.** Training trial clinicians (N=40) will be recruited from local mental health agencies as well as private practice. Trial clinicians will be naïve to exposure therapy and will self-select for the training.

### METHOD AND PROCEDURES:

**Overview.** This study will develop **SET™** based upon clinically-derived anxious behaviors by creating VP animations and learner interaction features to target and reduce therapist negative beliefs about exposure. An experimental therapeutics framework will be applied to a brief training trial to demonstrate initial engagement of our learning target (i.e., therapist negative beliefs about exposure).

#### Training Trial to Test Learning Target Engagement.

**Training Trial Overview.** Therapists seeking exposure training (N=40) will be recruited to complete a training workshop in exchange for continuing education credits (CEs) and monetary compensation. Therapists will be randomly assigned to interact with one of the **SET™** delivery methods (i.e., HMD or WB). All therapists will receive the same 4-hour didactic instruction in exposure therapy followed by experiential VR training (2 hours) with the assigned delivery method. Our learning target (negative beliefs) measure will be given at multiple timepoints to isolate the specific, incremental effect of the experiential component on our beliefs target (see Table 1). The two conditions will operate as a tandem case-series analysis that evaluates whether therapists in both conditions reach an a-priori target engagement benchmark.

**Training Trial Outcome Measures.** **Therapist Negative Beliefs about Exposure Scale (TBES)**. The TBES assesses the extent to which therapists endorse 21 negative beliefs about exposure therapy. The TBES is the primary outcome measure for assessing target engagement. **Exposure Knowledge**. We have condensed the original 49 multi-choice item measure by selecting 12 multiple-choice items that best fit the didactic content of our training. **Exposure Self-Efficacy**. This is a 27-item measure of therapists' confidence in delivering exposure therapy. This measure has demonstrated high internal consistency and predictive validity in determining the frequency of self-reported clinical use of exposure therapy.

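### Repeated TBES measurement cannot isolate the effect of SET over didactic training alone, because every therapist receives both in the same order and only the delivery medium is randomised

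*Combined protocol and SAP*

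**What the plan says.** All the design facts are in the protocol's section Training Trial to Test Learning Target Engagement, under the overview.

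- **Claim.** TBES is "given at multiple timepoints to isolate the specific, incremental effect of the experiential component on our beliefs target". The same section confirms its standing: "The TBES is the primary outcome measure for assessing target engagement".
- **Sequence.** "All therapists will receive the same 4-hour didactic instruction in exposure therapy followed by experiential VR training (2 hours) with the assigned delivery method".
- **Randomisation.** "Therapists will be randomly assigned to interact with one of the" SET delivery methods, HMD or WB. No group without SET, with delayed SET or with the reverse order is described.
- **Success criterion.** "The two conditions will operate as a tandem case-series analysis that evaluates whether therapists in both conditions reach an a-priori target engagement benchmark". The text gives no value for the benchmark.

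Subject Recruitment adds the population: 40 clinicians, of whom it says "Trial clinicians will be naïve to exposure therapy and will self-select for the training".

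The Analytic Plan lists 16 tests on the longitudinal measures: 8 within-condition changes from baseline, 4 cross-sectional comparisons of the conditions, and 4 comparisons of the conditions in change from baseline. Holm's method holds the familywise error at 0.05.

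**The concern.** To call an effect specific and incremental is to say what SET adds to didactic training. That needs some estimate of what the TBES would have done over the same interval without SET, and no therapist supplies one.

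Other things can move a self-reported belief score between the end of the didactics and the end of SET: answering the same 21 items again, delayed effects of four hours of teaching just completed, and the expectation of therapists who chose to come for this training. All are present in both arms, so comparing the arms does not reveal them, and measuring more often does not remove them.

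At stake is how the primary result is read. If SET added nothing, both arms could still improve after it, and under the protocol's wording that improvement would be reported as an effect isolated to SET.

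**Working it through.** The documents give no sample-size, power or effect figure on this point, so there is nothing of the plan's own to reproduce. The check has two parts.

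**1. What the design can estimate**

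Take the arrangement most favourable to the claim: TBES at baseline, after the didactics and after SET. Let *b* be the baseline mean, *D* the change up to the post-didactic form, *T* everything other than SET that moves the score over the SET interval, and *S_H* and *S_W* the SET effects by HMD and WB. The expected means are:

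| Occasion | HMD arm | WB arm |
|---|---|---|
| Baseline | b | b |
| After didactics | b + D | b + D |
| After SET | b + D + T + S_H | b + D + T + S_W |

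These are four distinct means for five unknowns (rank 4 of 5).

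- Change over the SET interval, HMD: T + S_H. WB: T + S_W. Both sums are estimable, but neither S_H nor S_W is.
- Difference between arms: (T + S_H) − (T + S_W) = S_H − S_W. This is estimable and protected by randomisation.

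A concurrent group with didactics only would add the mean b + D + T. The rank becomes 5 of 5 and both SET effects are then estimable. That is the missing piece. Further assessments in the same two arms do not supply it unless one also assumes something about T.

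The Analytic Plan does not help. Its within-condition tests start from baseline, so they estimate D + T + S and take in the didactic effect as well. Adding a contrast of post-SET with post-didactic scores would remove D but leave T.

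**2. An illustration of size**

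Assumptions, none from the documents: 20 per arm (the protocol gives N=40 but no allocation ratio), a true SET effect of zero, correlation *r* = 0.8 between post-didactic and post-SET TBES, a non-specific shift *d* in SD units of the score, and a two-sided paired t-test at an unadjusted 0.05.

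- Standard error of the change = √(2(1 − r)/n) = √(2 × 0.2/20) = 0.141 SD.
- Noncentrality = d/0.141 = 0.71, 1.41 and 2.12 for d = 0.1, 0.2 and 0.3.
- Rejection probability from the noncentral t with 19 degrees of freedom (critical value 2.093):

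| Shift d | r = 0.7 | r = 0.8 | r = 0.9 |
|---|---|---|---|
| 0.1 SD | 9% | 10% | 16% |
| 0.2 SD | 20% | 27% | 48% |
| 0.3 SD | 38% | 52% | 81% |

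With r = 0.8 and the strictest Holm threshold, 0.05/16 = 0.0031, the three figures fall to about 1.0%, 4.5% and 14%. The size therefore depends heavily on the threshold and on the assumed shift. Part 1 depends on neither.

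**The case against.** The best defence is that the trial's aim is modest. Method and Procedures speaks of initial engagement of the learning target, Research Objectives asks which platform offers the better balance, and the overview openly calls the design a case series against a benchmark. That is legitimate for an early study of 40 therapists. On this view, the disputed phrase only means separating the SET interval from the didactic interval in time, which a TBES form taken between them would do.

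Much of this stands: the design need not be abandoned, and the platform comparison is properly randomised. But separating intervals in time is not attributing change to a component. The phrase claims a specific effect, and the documents neither state nor defend the assumption of no other influence that this would require. Table 1, which should give the assessment times, is not shown, but no timing within these two arms would settle the matter.

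A reader might also infer more than the documents support:

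- **That no effect involving SET can be estimated.** Not so: HMD versus WB is randomised. What is not identified is SET against didactic training alone.
- **That the plan has a false-positive rate of 27% or so.** The contrast behind that figure is not among the 16 listed tests, the plan's 0.05 is familywise, and the shift and correlation are assumed.
- **That the chance of both arms wrongly meeting the benchmark can be calculated.** The text gives no benchmark value.
- **That outside training or practice contaminates later follow-ups.** The schedule cannot be seen. If the forms before and after SET fall within one workshop, calendar time matters little there, though repeat testing and expectation remain.

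**Conclusion.** The point holds for the effect of SET over didactic training alone. On its primary outcome the protocol claims a property that its design does not have. This follows from the fixed order, the lack of any group without SET and the randomisation between media only, all stated in the same section. It needs no numerical assumption.

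The size of any false attribution is unknown. About 10%, 27% and 52% for shifts of 0.1, 0.2 and 0.3 SD is an illustration under 20 per arm, a correlation of 0.8 and an unadjusted paired t-test. It is not a property of the planned analysis.

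The wording should be corrected, because it governs what the trial may conclude. The case-series design itself is not at fault.

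**What to change.** In the overview of Training Trial to Test Learning Target Engagement:

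1. Replace the stated purpose of the repeated TBES, isolating a specific and incremental effect, with: *to describe the change that follows the experiential component*.
2. Add that within-arm change and attainment of the benchmark are uncontrolled for repeat testing, delayed didactic effects and expectation, and cannot be attributed specifically to SET.
3. State that causal conclusions are confined to HMD versus WB.

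Carry the same limits into the report. The Analytic Plan is written in the past tense, so the analysis may already be complete, but these changes remain possible.

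The cost is a few sentences and a less favourable claim, with no added therapists, forms or visits. The one causal contrast left is also imprecise: with an assumed 20 per arm, the difference detectable with 80% power at an unadjusted two-sided 0.05 is about (1.96 + 0.84) × √(2/20) = 0.89 SD. The report should not read a null HMD-versus-WB result as equivalence.

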## Analytic Plan

Statistical analyses were carried out using SAS version 9.4 1M7 (The SAS Institute, Cary NC). Knowledge, Self Efficacy, and TBES were assessed longitudinally and analyzed via binomial Generalized Estimating Equations (GEE). SUS, VPE, and TARS were only assessed at the conclusion of the study and were analyzed using a binomial generalized linear model. Both sets of analyses used the binomial distribution to constrain the model space to the range of the measures being used. The scores were first shifted to have a minimum score of zero by subtracting the minimum score possible. This was used as the binomial number of “successes”, and the range of the score was used as the number of “trials”. Classical sandwich estimation was then used to better incorporate any differences in empirical variances and covariances. Both raw and adjusted (where appropriate) p-values were presented as well as unadjusted 95% confidence intervals. For GEEs, 16 different hypotheses were tested using orthogonal linear estimates: a) changes from baseline conditions in each condition (8 total), b) high- and low-immersion training conditions compared at each time point cross sectionally (4), and as c) condition comparisons in changes from baseline for each follow-up (4). The Holm test was used to calculate adjusted p-values maintaining familywise alpha at 0.05 across all 16 hypothesis tests in GEEs. For all other models, only one hypothesis was tested comparing the conditions.

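### With about 20 therapists per arm, an uncorrected sandwich and no stated reference distribution do not support the claim that Holm holds familywise alpha at 0.05

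*Combined protocol and SAP*

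**What the plan says.** The Analytic Plan fits binomial GEEs to Knowledge, Self Efficacy and TBES, and a binomial generalized linear model to three end-of-study measures: "SUS, VPE, and TARS were only assessed at the conclusion of the study and were analyzed using a binomial generalized linear model". On the variance it says: "Classical sandwich estimation was then used to better incorporate any differences in empirical variances and covariances". That sentence follows text about both sets of analyses, so it appears to cover the GEEs and the end-of-study models alike.

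On multiplicity it says: "The Holm test was used to calculate adjusted p-values maintaining familywise alpha at 0.05 across all 16 hypothesis tests in GEEs". On reporting it says: "Both raw and adjusted (where appropriate) p-values were presented as well as unadjusted 95% confidence intervals".

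The sample size is given under Subject Recruitment: "Training trial clinicians (N=40) will be recruited from local mental health agencies as well as private practice". The training trial section repeats the 40 and describes random assignment to two delivery methods. It does not state the allocation ratio. Neither the protocol nor the Analytic Plan names a finite-sample correction, a t or F reference, degrees of freedom or a SAS procedure. The training trial section makes TBES the primary measure of target engagement.

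**The concern.** Holm takes raw p-values as given and controls familywise error only if each is valid. A robust variance from about 20 independent therapists per arm has two small-sample problems, and both make p-values too small.

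- **Bias.** The uncorrected sandwich divides by n instead of n − 1, so the variance is low by the factor 19/20.
- **Reference.** A normal reference treats the estimated variance as known, although it rests on about 19 degrees of freedom within an arm and 38 between arms.

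Holm's first step lies far in the tail, where the normal and t distributions differ most in relative terms. The error is therefore proportionally larger there than at 0.05.

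At stake are the raw p-values, the Holm-adjusted p-values and the unadjusted 95% intervals for TBES, Knowledge and Self Efficacy, and probably the single comparisons of SUS, VPE and TARS. The a-priori benchmark in the training trial section is a separate question and is not affected by this point.

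**Working it through.** **Inputs from the documents.** N = 40 and two conditions (training trial section). 16 tests, alpha 0.05, Holm and the classical sandwich (Analytic Plan). The 8 within-condition tests over 2 conditions imply 4 follow-ups, so 5 time points with baseline.

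**Assumptions not in the documents.** 20 per arm (1:1 allocation), complete data, a saturated arm-by-time model, the 4 cross-sectional tests placed at the 4 follow-ups, the TBES score range, the within-therapist correlations and the reference distribution.

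**Step 1: the plan's own figure.** 8 + 4 + 4 = 16 tests. Holm's first step is 0.05/16 = 0.003125, and 16 × 0.003125 = 0.05. The stated familywise alpha is reproduced, provided the raw p-values are valid.

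**Step 2: size of each test.** In a saturated arm-by-time model the classical sandwich is the empirical variance with divisor n. The true size is therefore approximately

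P(|t_df| > c × √(19/20)), with df = 19 within an arm and 38 between arms,

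where c is the critical value applied. For z at 0.05, c = 1.960. Since √(19/20) = 0.975, the standard error is about 2.5% low.

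| SE and reference | Within arm, nominal 0.05 | Between arms, nominal 0.05 |
|---|---|---|
| Classical SE, z | 0.0713 | 0.0637 |
| Corrected SE, z | 0.0648 | 0.0574 |
| Classical SE, t(38) | 0.0632 | 0.0558 |
| Classical SE, t on own df (19 or 38) | 0.0555 | 0.0558 |

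At Holm's first step, the classical SE with z gives 0.0096 within an arm (0.0096/0.003125 = 3.1 times nominal) and 0.0065 between arms (2.1 times).

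**Step 3: which problem is larger.** The share of the excess at 0.05 that is due to the reference is (0.0648 − 0.05)/(0.0713 − 0.05) = 0.70 within an arm and (0.0574 − 0.05)/(0.0637 − 0.05) = 0.54 between arms.

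**Step 4: familywise error after Holm.** The tests are correlated, so this was simulated: binomial-logit GEE with all 16 contrasts, 40,000 trials per scenario (Monte Carlo SE about 0.0014), and exchangeable or AR(1) latent correlation of 0.4 or 0.7. Score ranges were 0–12 (one point for each of the 12 Knowledge items) and 0–84 (assumed for the 21-item TBES).

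| Variance and reference | All 16 nulls true | Only the 8 between-arm nulls true |
|---|---|---|
| Classical, z | 0.082–0.093 | 0.065–0.077 |
| Classical, t(152) | 0.074–0.084 | not reported |
| Classical, t(38) | 0.054–0.060 | 0.042–0.054 |
| Classical, t on 19/38 df | 0.042–0.045 | not reported |
| Corrected SE, z | 0.070–0.079 | not reported |
| Corrected SE, t on 19/38 df | 0.034–0.037 | not reported |

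Per-test size at nominal 0.05 under z was 0.069–0.071 within an arm and 0.060–0.065 between arms. With the classical sandwich and t on 19/38 df it was still about 0.053–0.057. With both corrections it was 0.047–0.051.

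**Step 5: sensitivity under z.** A separate simulation over correlations of 0.3 to 0.9 gave 0.078–0.093 with all nulls true and 0.059–0.077 with only the between-arm nulls true. The lowest values, 0.059–0.062, came at correlation 0.9. Other cases, all nulls true: 17 per arm gave 0.090–0.107, a 24/16 split gave 0.098, skewed or discrete scores gave 0.095–0.110, and normal-score approximations gave up to 0.099.

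**Step 6: end-of-study comparisons.** For SUS, VPE and TARS the between-arm closed form applies: size about 0.064 under z and 0.056 under t on 38 df.

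**The case against.** The strongest reply is that the plan never says z tests were used, and that the reference distribution matters more than the estimator. Keeping the classical sandwich and changing only the reference to 19/38 df brings familywise error to 0.042–0.045. The Holm sentence could then be true with the estimator exactly as written. On this view the plan has a reporting gap that one clarifying sentence could close.

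The range is also not firm. It drops slightly below 0.065 at very high correlation and exceeds 0.093 with smaller or unequal arms or skewed scores. The upper end needs no change in either arm at any follow-up, which is hard to believe after 4 hours of teaching and 2 hours of VR practice. Finally, the training trial section describes a tandem case series judged against a benchmark, and no stated decision depends on the Holm p-values.

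Much of this stands as a limit on size. The familywise figure is conditional on z. If both arms improve equally, the relevant range is the lower one. The benchmark is untouched.

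It does not remove the point. The plan asserts control at 0.05 without stating the choice on which control depends. Holm also gives no protection to the raw p-values and unadjusted intervals, which the plan reports. With the classical sandwich these remain anti-conservative under every reference examined: closed-form size is about 0.056 with t on own df, and 0.056 to 0.063 with t(38).

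**Conclusion.** The concern holds and should be fixed. As written, the plan does not support the claim that familywise alpha is maintained at 0.05. If Wald z tests were used, familywise error is about 0.065–0.093, and 95% intervals cover about 93% within an arm and 93.5–94% between arms. With a t(38) reference and the classical sandwich, familywise error is close to nominal, at most about 0.06 when all nulls are true and scores are near normal.

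Confidence in the direction and in the per-test sizes is high. The familywise range depends on the assumptions listed with the calculation. Dropout, unequal arms and skewed or ceiling-limited scores would raise it, and very high correlation would lower it a little. The excess is modest. It matters mainly for borderline results, including the comparison of the two delivery methods on TBES.

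**What to change.** Replace the classical sandwich with a small-sample-corrected one. State a t reference with degrees of freedom based on the number of therapists (about 19 within an arm and 38 between arms) for all GEE and GLM tests and intervals. Recompute the Holm p-values from those tests. Also state which reference distribution was used in the analyses already run.

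In the simulation, the Kauermann–Carroll correction with these degrees of freedom gave per-test size 0.047–0.051. Mancl–DeRouen was slightly conservative at 0.042–0.046. Other corrections, such as MBN, are available but were not evaluated here.

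The plan is written in the past tense, so the cost is a rerun of the GEE and GLM models, reissued p-values and intervals, and a short change to the text. No new data are needed. Relative to z with the classical sandwich, the standard error rises by about 2.6% (√(20/19) = 1.026), and the 95% multiplier rises from 1.96 to 2.09 (19 df) or 2.02 (38 df). Intervals become about 9% wider within an arm (2.09/1.96 × 1.026 = 1.09) and about 6% wider between arms (2.02/1.96 × 1.026 = 1.06). With both changes, familywise error with all nulls true is about 0.034–0.037, so the 0.05 claim would be supported at the cost of slight conservatism.

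### The 16 planned GEE tests leave out the post-experiential minus post-didactic TBES change within each condition, so the increment that the protocol sets out to isolate has no planned inference

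*Combined protocol and SAP*

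**What the plan says.** Under Training Trial to Test Learning Target Engagement, the sequence is the same for everyone: "All therapists will receive the same 4-hour didactic instruction in exposure therapy followed by experiential VR training (2 hours") by the assigned delivery method. The reason for repeating TBES is explicit: "Our learning target (negative beliefs) measure will be given at multiple timepoints" so as "to isolate the specific, incremental effect of the experiential component on our beliefs target". The same section states that "The TBES is the primary outcome measure for assessing target engagement", and describes a tandem case series that "evaluates whether therapists in both conditions reach an a-priori target engagement benchmark".

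The Analytic Plan then gives a closed list of 16 GEE hypotheses, with Holm adjustment at familywise 0.05:

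- (a) "changes from baseline conditions in each condition (8 total");
- (b) "high- and low-immersion training conditions compared at each time point cross sectionally (4");
- (c) "condition comparisons in changes from baseline for each follow-up (4").

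The raw and adjusted p-values and the 95% confidence intervals described there belong to these tests. The Analytic Plan does not mention the benchmark.

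**The concern.** The stated aim calls for the change in TBES from just after the didactics to just after the VR session, within each condition. No item on the list is that quantity. Every within-condition test starts from baseline, so its post-VR version credits SET with whatever four hours of teaching had already achieved. The Overview under Method and Procedures says the training trial is meant to demonstrate initial engagement of the negative-beliefs target. If a significant change from baseline is read as that demonstration, SET could be credited with an effect that came wholly from the didactics. The randomised HMD versus WB comparisons are not at risk, because both arms share the didactic session.

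**Working it through.** **1. Reproducing the count.** With one baseline, F follow-ups and two conditions, set (a) has 2F tests, (b) has F and (c) has F, so the total is 4F. F = 4 gives 8 + 4 + 4 = 16, as stated. This needs (b) to leave out the baseline comparison; including it would give 17. Three follow-ups with (b) at all four time points would give 6 + 4 + 3 = 13. Four follow-ups is therefore the reading that fits, but it is inferred.

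**2. What each set estimates.** Write m(c,t) for the mean of condition c at time t on the model's linear scale, with 0 = baseline, D = post-didactic and V = post-VR. The target is m(c,V) − m(c,D).

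- Set (a) at V: m(c,V) − m(c,0) = [m(c,V) − m(c,D)] + [m(c,D) − m(c,0)], that is, increment plus didactic effect.
- Set (b) at V: m(HMD,V) − m(WB,V). An increment common to both arms cancels.
- Set (c) at V: the between-arm difference of the set (a) changes. A common increment cancels again.

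Four follow-ups allow 6 follow-up-to-follow-up contrasts per condition, 12 in all. Writing the 16 tests as contrasts on the 10 condition-by-time means shows that none of the 12 is among them.

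**3. Can the increment be recovered from set (a)?** The point estimate can, on the linear scale, by subtraction. The standard error cannot. If two set (a) estimates each have standard error s and correlate r, the increment's SE is s√(2(1 − r)):

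| r | SE of increment |
|---|---|
| 0 | 1.41s |
| 0.5 | 1.00s |
| 0.7 | 0.77s |
| 0.9 | 0.45s |

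The plan does not say that r, or the covariance, will be reported.

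**4. How far a change from baseline can mislead.** Illustration only. N = 40 is in the protocol; 20 per arm is assumed, since no allocation ratio is given. A paired t-test stands in for the GEE and the true VR effect is set to zero. The documents give no didactic effect, so a range is used, in SD units of the change score. The noncentrality is d√20 with 19 degrees of freedom. The first Holm step is 0.05/16 = 0.003125.

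| Didactic change d | P(significant) at 0.05 | at 0.003125 |
|---|---|---|
| 0.3 | 0.247 | 0.039 |
| 0.5 | 0.565 | 0.167 |
| 0.75 | 0.889 | 0.507 |
| 1.0 | 0.989 | 0.840 |

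Later Holm steps are less strict, so the true operating level lies between the two columns.

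**5. What adding the contrasts costs.** Increment detectable with 80% power (paired t, n = 20):

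| Alpha | Where it arises | Detectable d |
|---|---|---|
| 0.05 | unadjusted | 0.66 SD |
| 0.05/2 = 0.025 | first step, separate two-test family | 0.74 SD |
| 0.05/16 = 0.003125 | first step, family of 16 | 0.96 SD |
| 0.05/18 = 0.00278 | first step, enlarged family | 0.97 SD |

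**The case against.** The strongest reply is that the schedule cannot be seen. Table 1 is not in the text available and the Analytic Plan does not define baseline. If baseline meant the post-didactic score, set (a) would already contain the contrast. Nothing in the documents says so, and repeating the measure to separate the experiential part from the didactics makes little sense without a score taken before both. The dependence is real, but the natural reading goes against the plan.

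The design's stated evaluation is attainment of a benchmark, and no sentence demands a p-value for the increment. That is fair. However, the benchmark's value and reference time are not in the text and no planned analysis addresses it, so it cannot be shown to fill the gap.

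If TBES was taken after the didactics, set (a) also reports the post-didactic change, so a careful reader can see roughly how much came before the VR session. This stands for the point estimate but not for its uncertainty.

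Finally, with no didactic-only arm, the increment still mixes in retest and time effects. This also stands. It limits how the contrast may be described, but the contrast is still closer to the stated aim than a change that includes four hours of teaching.

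**Conclusion.** The concern holds. Followed as written, the plan gives no standard error, confidence interval or p-value for the effect that repeated TBES measurement was designed to isolate. The tests it does give for each condition do not separate SET from the didactics. The probability of a significant post-VR change with no VR effect runs from 0.04 to 0.99 over the didactic effects and significance levels considered; this is an illustration of scale, not a prediction.

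The conclusion rests on two assumptions that the protocol implies but does not state in the text available: baseline precedes the didactics, and TBES was also taken after them. No data are lost, because the fitted model can already supply the contrast. Because the gap concerns the primary outcome and is so cheap to close, it should be fixed.

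**What to change.** - Add to the TBES model one linear estimate per condition, post-experiential minus post-didactic, as the primary estimate of SET target engagement, with its SE and 95% CI.
- Define baseline and name the assessment times in the Analytic Plan.
- Describe changes from baseline as effects of the whole workshop.
- State where the two contrasts sit: as a separate primary pair with Holm across the two (first step 0.025), or inside the TBES family, enlarged to 18 (first step 0.00278).
- State how the contrasts relate to the a-priori benchmark.
- Report the increment as a within-arm change that may include retest and time effects. A between-arm difference in the increment is optional.
- The Analytic Plan is written in the past tense. If results already exist, label these contrasts as added after the original plan.

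The cost is two estimates and some SAP wording, with no new participants or data if the post-didactic TBES was collected. Joining the Holm family lowers its first-step threshold from 0.003125 to 0.00278 and raises the detectable increment at that step to 0.97 SD; a separate pair keeps it at 0.74 SD and leaves the existing 16 thresholds unchanged.
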